Appendix 1. Schedule of Events (Recipient)

Transplant Study Day		-1	0	12										Unscheduled Visit within 3 months of transplant	Unscheduled Visit greater than 3 months from transplant		
Transplant Study Week					4-6												
Transplant Study Month						2	3	6	9	12	18 ⁶	24 ⁶	25-54 ⁶				
Visit Number		00	01	02	03	04	05	06	07	08	09	10					
Informed Consent, Screening	Original retained, copy provided to study participant	X															
Assessment of Eligibility Criteria	Enrollment and Randomization Inclusion/Exclusion Criteria	X	X														
Demographics	Date of birth, Race, Ethnicity and Gender	X															
Medical and Respiratory History	Body Systems	X															
Physical Exam	Height, weight, temperature, blood pressure, pulse, heart rate, screening neurological assessment		X	X	X	X	X	X	X	X	X	X	X	X	X		
Pulmonary Function Test	Age Restrictions (collect if performed as standard of care)	X		X	X	X	X	X	X	X	X	X	X	X	X		
Imaging	Chest X-Ray, Chest CT, Perfusion Scan (collect if performed as standard of care)			X	X	X	X	X	X	X	X	X	X	X	X		
Medications	Concomitant, Immunosuppressive and Prophylactic Medications	→	→	→	→	→	→	→	→	→	→	→	→	→	→		
Assessments of Events	AE/SAE, PGD, Infection, Rejection, Hospitalization, PTLD, or Re-transplant	→	→	→	→	→	→	→	→	→	→	→	→	→	→		
Assessment of Endpoint Events	Chronic Allograft Dysfunction, Death, Re-Listed	→	→	→	→	→	→	→	→	→	→	→	→	→	→		
Blood Type/HLA Typing	A, B, O, Rh factor, Class I (A, B, C), Class II (DR, DP, DQ) if available	X															
Panel Reactive Antibody	Current	X															
PRA	Highest PRA or cPRA (within 12 weeks of transplant)		X														
Crossmatch	T cell and B cell		X														
Pregnancy Test	Serum or Urine (within 48 hours of transplant)		X		X		X	X	X	X	X						
Hematology Panel	CBC (including differential and platelets)		X	X	X	X	X	X	X	X	X	X	X	X	X		
Trough Levels	Tacrolimus (all tacrolimus trough levels collected as SOC will be collected after 3 months post-transplant)		X	X	X	X	X	X	X	X	X	X	X	X	X		
Chemistry Panel	Glucose, BUN, creatinine, uric acid, total bilirubin, alkaline phosphatase, LDH, total protein, SGOT (AST), SGPT (ALT), calcium	X	X	X	X	X	X	X	X	X	X	X	X	X	X		
CMV/EBV	Only collect if performed as standard of care, serology collected at baseline and viral	X	X	X	X	X	X	X	X	X	X	X	X	X	X		

Transplant Study Day		-1	0	12																						Unscheduled Visit within 3 months of transplant	Unscheduled Visit greater than 3 months from transplant
Transplant Study Week					4-6																						
Transplant Study Month						2	3	6	9	12	18 ⁶	24 ⁶	25-54 ⁶														
Visit Number		00	01	02	03	04	05	06	07	08	09	10															
	load at post-transplant visits																										
Serology	HIV, HBsAg, HBCAb, HCV Ab (within 12 months of transplant)	X																									
Immunoglobulin Levels	IgG	X	X	X	X	X	X	X	X	X	X	X													X	X	
Pathology	Local Biopsy Histology Scoring (ISHLT), including c1q fixation and C4d			X	X		X	X	X	X	X														X	X	
	Rituximab or Placebo (375 mg/kg)		X	X																							
HUMORAL ANTIBODY CORE – WUSTL (PI: [name])																											
	Serum- Anti-HLA Ab, Non-HLA Ab, Crossmatch Testing	X	X	X	X	X	X	X	X	X	X	X														X	X
	Serum- Autoantibodies	X	X	X	X	X	X	X	X	X	X	X														X	X
MARKERS OF GRAFT INJURY CORE – WUSTL (PI: [name])																											
	Serum- Cytokine/Chemokine/GF				X		X	X	X	X	X	X														X	X
	Bronchoalveolar Lavage (BAL) – Supernatant for Cytokine Analysis		X	X	X		X	X	X	X	X															X	X
MOLECULAR IMMUNOLOGY CORE – ISMMS (PI: [name])																											
	Blood-mRNA Profiling, Gene Exp.				X		X	X	X	X	X	X															
	Bronchoalveolar Lavage – Pellet for Gene Expression Profiles		X	X	X		X	X	X	X	X															X	X
	RNA Sequencing for IgG VDJ Regions ([name], Emory)							X	X	X	X																
CELLULAR IMMUNOLOGY CORE – ISMMS (PI: [name])																											
	Blood- T and B Cell Phenotyping (Flow Cytometry)	X			X		X	X		X	X																X
	Bronchoalveolar Lavage –in Cell Preservative: Phenotyping B Cells		X	X	X		X	X	X	X	X															X	X
	T Cell Function (ELISPOT) and Plasma to Archive	X						X		X	X																X
IMMUNOHISTOCHEMISTRY CORE –ISMMS (PI: [name])																											
	Immunohistochemistry: CD4, FoxP3, CD20 and CD8, CD20 and CD68: (5 unstained slides: Minimum of 3 slides prepared with 2 sections each representative of more than one tissue section)			X	X		X	X	X	X	X															X	X
VIRAL DETECTION CORE –WUSTL (PI: [name])																											
	Bronchoalveolar Lavage – Whole specimen for Viral Detection		X	X	X		X	X	X	X	X															X	X
	Nasal Swab-Viral PCR		X	X	X		X	X	X	X	X															X	X
	Whole Blood Quantitative Viral Studies (CMV/EBV)	X	X	X	X	X	X	X	X	X	X	X														X	X

Transplant Study Day		-1	0	12										Unscheduled Visit within 3 months of transplant	Unscheduled Visit greater than 3 months from transplant	
Transplant Study Week					4-6											
Transplant Study Month						2	3	6	9	12	18 ⁶	24 ⁶	25-54 ⁶			
Visit Number		00	01	02	03	04	05	06	07	08	09	10				
BIOSPECIMEN REPOSITORY – ISMMS (PI: [name])																
Blood to Archive		X														
	
 1. Visit 00: Samples may be collected up to 60 days prior to transplant surgery. 2. Visit 01: Samples may be collected up to 72 hours following transplant. 3. Visit 02: Samples may be collected 1-2 weeks after transplant. 4. Visit 07: The month 9 visit will occur if the subject is seen as part of the local standard of care at this timepoint. 5. Unscheduled Visits: BAL obtained if performed by the clinical site for diagnostic purposes. For visits occurring greater than 3 months blood will be collected if visit is conducted at the transplant center. 6. All subjects will complete 12 months of follow-up. A sub-set of subjects will also complete Month 18 – Month 54 visits. 															

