Thus our primary hypothesis is that induction with rituximab (in combination with Thymoglobulin) will improve outcomes following pediatric lung transplantation through a decrease in antibody development post-transplant.

The regimen of 375mg/m² was chosen based on manufacturer labeling for current indications, safety profile and historical pediatric experience with rituximab. In light of the information from prior studies using a single dose of rituximab a second dose is scheduled at day 12 post-transplant consistent with the study design of the adult heart transplant study (CTOT-11). We will assess the level of B cell reduction in the first 8 participants using flow cytometry to ensure B cell reduction in this patient population is equivalent to B cell reduction obtained in other studies.

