6.1.1.2. Dosage and Preparation

Rituximab will be given as an intravenous infusion.

2 Doses: 375 mg/m² on Day 0 (within 12 hours of return to ICU following transplant) and Day 12 (+/- 2 days).

Rituximab should be prepared using appropriate aseptic techniques. Withdraw the necessary amount of Rituximab or Rituximab Placebo and dilute to a final concentration of 1 to 4 mg/mL into an infusion bag containing either 0.9% Sodium Chloride, USP, or 5% Dextrose in Water, USP. Gently invert the bag to mix the solution. Discard any unused portion left in the vial. Parenteral drug products should be inspected visually for particulate matter and discoloration prior to administration.

Rituximab or Rituximab Placebo should be given as a **slow** intravenous infusion. **It should not be administered as an intravenous push or bolus.** Do not infuse rituximab concomitantly with another IV solution or other IV medications. Rituximab infusions should be made through a dedicated line.

Participants will be premedicated using:

- Tylenol® (Acetaminophen), 15 mg/kg (to a maximum of 1 gram) should be administered (by mouth, enteral or rectal administration) 30 to 60 minutes prior to the start of an infusion; and
- Benadryl® (Diphenhydramine) by mouth 30-60 minutes prior to the start of an infusion as described in **Table 1** or by IV 1 mg/kg (to a maximum of 50 mg) 30 minutes prior to the start of an infusion.

Age (years)	Diphenhydramine Oral Dose (mg)
2-6	6.25
6-<12	12.5
12+	25

Table 1: Diphenhydramine Pre-medication Dose

Premedication may attenuate infusion-related events. Since transient hypotension may occur during rituximab infusion, consideration should be given to withholding anti-hypertensive medications 12 hours prior to rituximab infusion.

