6.1.1.3. Administration Guidelines

First infusion (Day 0): Rituximab should be administered within 12 hours of returning from the ICU following transplant, based on hemodynamic stability. Rituximab should be administered intravenously through a dedicated line at an initial rate of 0.5 mg/kg/hr (to a maximum rate of 50 mg/hr) for the first hour.

If hypersensitivity or infusion-related events do not occur, the infusion rate will be escalated by 0.5 mg/kg/hr every 30 minutes, to a maximum rate of 400 mg/hr.

If a hypersensitivity or infusion-related reaction event develops, the infusion rate should be temporarily slowed or interrupted. The infusion can continue at one-half the previous rate upon improvement of patient symptoms.

Subsequent Infusion (Day 12 +/- 2 days):

A second dose of rituximab will be administered to subjects considered stable enough to receive the infusion.

Individual Subject Stopping Rules:

Individuals who meet any of the criteria listed below will not receive the second dose of rituximab.

1. Serious adverse event causally related to the rituximab infusion;
2. Acute pulmonary infectious process with evidence of graft dysfunction;
3. Positive blood culture, sepsis or other disease process with hemodynamic instability;
4. Renal insufficiency requiring hemodialysis or ultrafiltration;
5. Inability to obtain intravenous access;
6. Use of an investigational drug after the first dose of placebo or rituximab;
7. Any other event which in the opinion of the principal investigator may pose additional risk to the participant.

If the first infusion was well tolerated, the subsequent infusion may be administered intravenously through a dedicated line at an initial rate of 1.0 mg/kg/hr (to a maximum rate of 100 mg/h) for the

first hour. If hypersensitivity or infusion-related events do not occur, the infusion rate will be escalated by 1.0 mg/kg/hr (maximum rate of 100 mg increase per hour) every 30 minutes, to a maximum rate of 400 mg/hr. If hypersensitivity or infusion-related event develops, the infusion should be temporarily slowed or interrupted. The infusion can continue at one half the previous rate upon improvement of patient symptoms.

If hypersensitivity or infusion-related events occurred during the first infusion, the subsequent infusion should be administered in the same manner as the first infusion.

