8.3. Randomization

Eligibility for randomization will be confirmed. Hematology (CBC with differential and platelet count) and serum chemistries will be obtained within 2 weeks of randomization.

Randomization will occur within 12 hours after returning to the ICU following transplant.

Randomization will only occur if there are still spaces available at the time of transplantation. If the targeted accrual has been reached at the time of transplantation the participant will be excluded from further procedures and randomization.

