8.6. Visit Windows

Study visits should take place within the time limits specified below: the designated visit windows (*i.e.* +/- *n* days) for each scheduled visit are also indicated on the Table of Events.

Visit No.	Visit	Visit Window
00	Baseline	Pre-transplant blood may be collected up to 60 days prior to transplant surgery. Blood must be recollected every 60 days.
01	Transplant	Infusion within 12 hours of returning to the ICU following transplant Labs within 72 hours of transplant
02	Day 12	+/-2 days
03	Week 4-Week 6	+6/- 7 days
04-05	Month 2-Month 3	+/- 7 days
06-07	Month 6-Month 9	+/- 14 days
08-10	Month 12-Month 24	+/- 30 days

Table 11: Visit Windows

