6.2. Treatment Adherence

Treatment Groups:

- **Rituximab Group** – induction therapy with anti-CD20 mAb (375 mg/m²) IV on day 0 and day 12 post-transplant plus standard of care immunosuppression (thymoglobulin induction, tacrolimus or equivalent, MMF or equivalent, and steroids).
- **Placebo Group** – induction therapy with placebo IV on day 0 and day 12 post-transplant plus standard of care immunosuppression (thymoglobulin induction, tacrolimus or equivalent, MMF or equivalent, and steroids).

Randomization to one of the two groups will occur once the subject has received the transplant and is deemed hemodynamically stable. The first infusion must be administered within 12 hours of returning to the ICU following transplant. The second infusion should be administered on day 12 (\pm 2 days) post-transplant.

Adherence will be summarized for the ITT sample. The status of each infusion will be classified as complete, partial, or not done and the duration (or extent) of exposure will be calculated by determining the number of days between first and second infusions (+1) for each subject in the

sample. These variables will then be summarized using appropriate statistics in a table and subject-level details will be presented in a listing.

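### The Schedule of Events prints the study dose as 375 mg/kg instead of 375 mg/m², about 16 to 40 times the intended dose at assumed body sizes

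*Protocol*

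**What the plan says.** Appendix 1 of the protocol (recipient schedule) has one row for study drug, marked at visit 01 (day 0) and visit 02 (day 12): "Rituximab or Placebo (375 mg/kg". None of its footnotes qualifies the dose or refers the reader to another section.

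The section on dosing and preparation, 6.1.1.2, specifies two doses, the first being "375 mg/m² on Day 0 (within 12 hours of return to ICU following transplant". The rationale in section 2.2 supports the same unit: "The regimen of 375mg/m² was chosen based on manufacturer labeling for current indications". The SAP, section 6.2, describes the active arm as "induction therapy with anti-CD20 mAb (375 mg/m²) IV on day 0 and day 12 post-transplant". The Protocol Synopsis, Protocol section 3.1 and the SAP synopsis (section 1) also give 375 mg/m².

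Three other places have smaller slips of the same kind:

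- **Timing of the first infusion.** Section 6.1.1.3 says "Rituximab should be administered within 12 hours of returning from the ICU following transplant". Section 8.3 says "Randomization will occur within 12 hours after returning to the ICU following transplant", and Table 11 in section 8.6 says "Infusion within 12 hours of returning to the ICU following transplant".
- **IgG threshold.** It is 400 grams per dL in enrollment exclusion 8 (Protocol Synopsis, Protocol 4.3 and SAP section 1) and in randomization criterion 1 of Protocol 4.4. It is 400 milligrams per dL in randomization criterion 1 of the Protocol Synopsis and of SAP section 1, and in Protocol 7.4.
- **IVIG.** Section 7.4 first gives 400-500 mg/kg every four weeks, then states the maintenance dose as 400-500 mg/dL.

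**The concern.** A schedule of events is the table site staff use to see what happens at each visit. Here it carries a dose that contradicts the dosing section, and no clause says which prevails. Three features of the trial add to the concern. Section 4.2 sets an upper age of 21 years and no lower limit, so infants can be enrolled. The first infusion is due within 12 hours of arrival in the ICU. Only the research pharmacist knows the assignment, so bedside staff cannot check the dose against the drug. Section 15.1 also makes any departure from the protocol a deviation, and a protocol with two doses gives no clear standard for judging one.

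The smaller slips matter less. Read literally, section 6.1.1.3 starts the dosing clock when the patient leaves the ICU. Exclusion 8 would catch every candidate, because no serum holds 400 g of IgG per dL. The criterion in section 4.4 could still be met, since the age-normal limit is an alternative there.

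**Working it through.** **1. Count the dose statements.** Study dose of 375 mg/m²: Protocol Synopsis, 2.2, 3.1 and 6.1.1.2; SAP section 1 and section 6.2. That makes six. Study dose of 375 mg/kg: Appendix 1 only. Two further mentions, the earlier adult series in Protocol 2.4 and the rescue regimen for humoral rejection in 7.5.2, are also in mg/m². They are not counted because they are not the study dose. Nothing supports a mg/kg dose, and a lost superscript would not turn m² into kg.

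**2. Size of the error.** The documents give no heights or weights, so the body sizes below are assumptions.

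- BSA = √(height in cm × weight in kg / 3600)
- Ratio = (375 × weight) / (375 × BSA) = weight / BSA

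| Assumed size | BSA (m²) | 375 mg/m² | 375 mg/kg | Ratio |
|---|---|---|---|---|
| 3.5 kg, 50 cm | 0.220 | 83 mg | 1,313 mg | 15.9 |
| 10 kg, 75 cm | 0.456 | 171 mg | 3,750 mg | 21.9 |
| 20 kg, 115 cm | 0.799 | 300 mg | 7,500 mg | 25.0 |
| 60 kg, 165 cm | 1.658 | 622 mg | 22,500 mg | 36.2 |
| 80 kg, 180 cm | 2.000 | 750 mg | 30,000 mg | 40.0 |

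The top row of sizes is not a bound: at 100 kg and 175 cm, BSA is 2.205 m² and the ratio is about 45.

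**3. Could the printed dose be given?** Section 6.1.1.2 tells staff to "dilute to a final concentration of 1 to 4 mg/mL into an infusion bag". At the strongest permitted concentration the volume is 375 / 4 = 93.75 mL/kg, whatever the patient's size.

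Section 6.1.1.3 runs the first infusion at 0.5 mg/kg/hr (at most 50 mg/hr) for one hour, then adds 0.5 mg/kg/hr every 30 minutes up to 400 mg/hr.

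- **10 kg, 3,750 mg.** The rate is 5 mg/hr for the first hour and rises by 5 mg/hr each half hour. After 27.5 h, 3,715 mg has been given. The last 35 mg at 275 mg/hr takes 0.13 h, a total of 27.6 h.
- **10 kg, 171 mg.** After 6.0 h, 167.5 mg has been given. The rest takes about 0.06 h, a total of 6.1 h.
- **60 kg, 22,500 mg.** The rate starts at 30 mg/hr and reaches 390 mg/hr. After 7 h, 1,380 mg has been given. The remaining 21,120 mg at 400 mg/hr takes 52.8 h, a total of 59.8 h.
- **60 kg, 622 mg.** After 4.5 h, 555 mg has been given. The rest at 270 mg/hr takes about 0.25 h, a total of just under 5 h.

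With the 500 mg vials described in section 6.1.1.1, 22,500 mg is 22,500 / 500 = 45 vials.

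**4. IgG unit.** 400 g/dL = 400,000 mg/dL, which is 1,000 times 400 mg/dL.

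**The case against.** The strongest reply is that this is an erratum and no more. Preparation is governed by section 6.1.1.2, which is correct, and section 6.1.2.2 sends placebo dosing there too. The text cites Appendix 1 for visits, samples and examinations, not for calculating a dose. The error also reveals itself: nobody would draw up 45 vials or plan a 60-hour infusion. The fold range rests on assumed body sizes and describes a dose that could hardly be given. The other slips are plain from context: an IgG level of 400 g/dL is physically impossible, and section 7.4 states the correct IVIG unit in the same paragraph.

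Much of this stands. The intended dose is clear, the fold figures measure the misprint rather than a likely exposure, and the minor slips would not by themselves justify raising the point. The reply does not remove the case for correction. The row is current text in the schedule itself. The expectation that a pharmacist would catch it is a presumption, since the documents name a research pharmacist but describe no dose check. A dose that looks absurd lowers the chance of harm, but that is no reason to leave it in a pediatric protocol.

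**Conclusion.** The concern holds. The Appendix 1 dose unit is wrong and should be corrected. This conclusion rests on the dose row alone and needs no assumption, because six statements of the study dose contradict one. Only the size, about 16- to 40-fold, depends on the assumed heights and weights. Actual harm is unlikely given section 6.1.1.2 and the impracticality of the printed dose. Nothing in the sample size, the endpoints, the per-protocol definition or the analysis changes.

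**What to change.** Change the Appendix 1 row to 375 mg/m² and notify sites and research pharmacists directly. In the same clarification:

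- **Section 6.1.1.3:** count the 12 hours from the patient's return to the ICU.
- **IgG threshold:** print 400 mg/dL in enrollment exclusion 8 (Protocol Synopsis, Protocol 4.3 and SAP section 1) and in criterion 1 of Protocol 4.4.
- **Section 7.4:** state the IVIG maintenance dose as 400-500 mg/kg.

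The cost is one clarification letter or administrative amendment, with no change to the design or the analysis.

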6.2. Infusion Supervision (Rituximab and Rituximab Placebo)

Rituximab and rituximab placebo should be administered in a hospital environment where full resuscitation facilities are immediately available. Rituximab and rituximab placebo may be administered on an outpatient basis however patients may be hospitalized for observation at the discretion of the investigator.

The infusion will be supervised by the clinical staff (i.e., clinical nurse, physician) at the participating institutions. A history of each infusion and any adverse side effects will be recorded and reported to the SACCC using the appropriate case report forms.

Vital signs (temperature, blood pressure, pulse, and respiratory rate) and standard laboratory testing (CBC, basic metabolic panel) will be obtained prior to the start of each rituximab or rituximab placebo infusion. The local investigator will determine whether to hold the infusion due to lab abnormalities. Vital signs will be monitored every 15 minutes for the first hour of the infusion, every hour until the end of the infusion, and every hour thereafter for a total of 3 hours after the infusion. The IV line should remain in place for at least 1 hour following the infusion to enable the administration of drugs, if necessary. Additional vital signs may be obtained as clinically indicated. Fluid resuscitation will be provided as needed for changes in vital signs suggesting hydration would be beneficial.

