8.2. Screening/Baseline Visit

At the time of listing, potential participants will be entered on a site specific screening log. Age at listing, diagnosis and reason the patient was not enrolled into the study, if applicable, will be captured on the screening log. If the patient and/or parent(s)/guardian(s) are in agreement to participate in the study then the informed consent document should be obtained while the participant is on the wait list.

During the screening period study personnel will review the subject's medical record for previous and current medical history, perform a physical examination, and record the subject's demographic information (age, gender, and race). Blood specimens will be obtained for screening and mechanistic studies as specified in Appendix 1. Pre-transplant blood may be collected up to 60 days prior to transplant surgery. Blood must be recollected every 60 days until the transplant occurs.

The baseline visit will occur at the time of transplant. During the baseline visit, donor demographics (age, gender, and race), cause of death, HLA, Blood Type, serum creatinine, cytomegalovirus (CMV), Epstein - Barr virus (EBV), Hepatitis B, Hepatitis C, and HIV information will be collected.

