8.4. Clinical Laboratory Evaluation

Clinical laboratory measurements include serum chemistry and hematology. Results will be converted to standardized units where possible. For numeric laboratory results, descriptive statistics of laboratory values and the change from baseline of laboratory values will be summarized for each treatment group and overall. For any categorical laboratory results, the number and percentage of subjects reporting each result will be presented for each treatment group and overall.

In addition, or in lieu of summary statistics, clinical laboratory data may be plotted to show patterns over time. For each test with a numeric result, data will be plotted as a spaghetti plot where each subject's values will be plotted and connected by line segments, forming one line per subject. Tests with qualitative results will not be plotted.

Separate listings of laboratory data over time may also be created.

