8.5. Vital Signs, Physical Findings, and Other Observations Related to Safety

8.5.1. Vital Signs

Descriptive statistics of vital sign measures will be summarized by time point for each treatment group and overall. Since pre-infusion (i.e., baseline) vitals are not collected, no summary of change from baseline will be presented. Additionally, or in lieu of summary statistics, vital sign measures may be plotted over time by treatment group with individual lines for each subject.

Separate listings of vital sign data over time may also be created.

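### The protocol requires vital signs and blood counts before each infusion, but the SAP does not ensure that they serve as the safety baseline

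*Protocol*

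**What the plan says.** **Measurements required around the infusion.** Protocol 6.2 lists four vital signs and then says that "standard laboratory testing (CBC, basic metabolic panel) will be obtained prior to the start of each rituximab or rituximab placebo infusion". Vitals follow every 15 minutes in the first hour, hourly to the end of the infusion, and hourly for three hours afterwards.

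**What the SAP does with them.**
- Vital signs (SAP 8.5.1): "Since pre-infusion (i.e., baseline) vitals are not collected, no summary of change from baseline will be presented".
- Laboratory values (SAP 8.4, which covers serum chemistry and hematology): "the change from baseline of laboratory values will be summarized for each treatment group". The section does not name the baseline record.

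**What counts as baseline in the protocol.** Section 8.2 places the baseline visit at transplant. Table 11 in section 8.6 gives the label Baseline to visit 00, which precedes transplant by up to 60 days.

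**When scheduled samples are drawn.**
- Visit 01: Table 11 says "Labs within 72 hours of transplant", and Appendix 1 footnote 2 says "Visit 01: Samples may be collected up to 72 hours following transplant".
- Visit 02: Appendix 1 footnote 3 says "Visit 02: Samples may be collected 1-2 weeks after transplant", while Table 11 allows day 12 plus or minus 2 days.
- In Appendix 1 the CBC row is blank at visit 00 and starts at visit 01. Chemistry and IgG are marked at visit 00.

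**When the drug is given.** Sections 6.1.1.2 and 8.6 and SAP 6.2 allow 12 hours for the first infusion, counted from return to the ICU. Section 6.1.1.3 says "Rituximab should be administered within 12 hours of returning from the ICU following transplant". The second infusion is due on day 12 plus or minus 2 days.

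**The concern.** A change from baseline measures a drug effect only if the baseline precedes the drug. If a programmer takes the first scheduled CBC as baseline, some baselines may be drawn after the first infusion. Any early effect of rituximab on the counts would then be subtracted out in the rituximab arm. Thymoglobulin is given in both arms and would not create that difference by itself.

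Two features of adverse event collection in protocol 12.3.1 make these summaries more important than usual:
- From the first infusion until 6 weeks after the last, only cytopenias that meet serious criteria are collected. Non-serious grade 3 or 4 cytopenias in that window are visible only in the laboratory summaries. The same section defines a treatment-emergent laboratory event by a rise in grade from baseline.
- Grade 1 and 2 events are not collected at all. Change in vitals from before to during the infusion is therefore a useful measure of milder infusion reactions. Safety and tolerability is a stated secondary objective (section 1.3), yet the SAP drops this summary for a reason that section 6.2 contradicts.

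**Working it through.** The plan states no figure to reproduce. The check compares the time windows and then asks which pre-drug records exist.

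**1. Visit 01 against the first infusion.** Inputs: samples up to 72 h after transplant (Appendix 1, footnote 2); infusion start no later than 12 h after ICU return (6.1.1.2, Table 11). Let r be the hours from the transplant reference time to ICU return. The documents do not give r, so a range of 0 to 12 h is assumed.
- Permitted hours after the latest infusion start = 72 − (r + 12) = 60 − r.
- r = 0: 60 h, and 60/72 = 83%.
- r = 12: 48 h, and 48/72 = 67%.

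No text ties the visit 01 draw to the start of the infusion. These are shares of permitted time. They do not estimate how many samples will be post-drug.

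**2. Visit 02 against the second infusion (days 10 to 14).**
- Footnote 3, days 7 to 14: from 7 − 14 = −7 days to 14 − 10 = +4 days relative to the dose.
- Table 11, days 10 to 14: from 10 − 14 = −4 days to 14 − 10 = +4 days.

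The two sampling windows differ. Under either one, a visit 02 sample can fall before or after the dose.

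**3. Candidate baseline records.**

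| Record | Before the first infusion? | In Appendix 1? |
|---|---|---|
| Visit 00 chemistry and IgG | Yes | Yes |
| Visit 00 CBC | – | Not marked |
| Section 8.3 CBC and chemistries, within 2 weeks of randomization | Direction not stated | Not as such |
| Section 6.2 pre-infusion CBC and metabolic panel | Yes | Not as such |
| Visit 01 CBC and chemistry | Not assured | Yes |

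For chemistry and IgG, a scheduled value precedes the drug. For hematology, the first scheduled value may not. The section 6.2 CBC does precede it, but no text says that its result is entered in the database or is the baseline for SAP 8.4.

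**4. Vitals.** Section 6.2 obtains them before each infusion; SAP 8.5.1 says they are not collected. Either the SAP is mistaken, or a required measurement never reaches the study database. If the second is true, the section 6.2 CBC may not reach it either, because the same sentence requires both.

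**The case against.** The strongest reply is that pre-drug values are mandated. Section 6.2 requires a CBC and metabolic panel before each infusion, and enrollment needs neutrophil, platelet and hemoglobin values (section 4.2). Chemistry, IgG, serum antibodies and blood flow cytometry are all marked at visit 00. This stands. A reader might infer that safety changes in general have no pre-drug baseline, and the documents do not support that.

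Other stronger readings also fail:
- **Lavage changes understated.** Lavage sampling starts at visit 01, but SAP 8.4 covers only serum chemistry and hematology. No lavage change from baseline is planned.
- **Visit 02 as a contaminated baseline.** Visit 02 is never a baseline. The window mismatch is a point of wording to align.
- **No neurological comparator.** Section 8.2 tells staff to "perform a physical examination, and record the subject's demographic information", while the Appendix 1 examination row, which carries the neurological screen, is blank at visit 00. But the SAP plans only listings of neurological findings, so no planned comparison is lost.
- **Vitals as the only record of mild reactions.** Section 6.2 also has side effects of each infusion reported to the coordinating center. SAP 8.5.1 still summarises vitals by arm and time point.

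SAP 8.4 also summarises laboratory values themselves by arm, so later differences in level stay visible whichever baseline is used. Section 5.1 cites grade 3 or 4 lymphopenia in 40% and neutropenia in 6%. Those figures do not come from this population and give no onset within 72 hours, so they cannot size any bias here. It is also possible that SAP 8.5.1 describes the database rather than the bedside. Even so, the two texts need reconciling, because the data would then be measured and not kept.

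**Conclusion.** The concern holds in a limited form. Pre-drug vitals and blood counts should exist under section 6.2, but the SAP does not ensure that they are analysed as baseline. For vitals, SAP 8.5.1 omits a summary on a premise that conflicts with the protocol. For laboratory values, SAP 8.4 leaves baseline undefined, and the first CBC in Appendix 1 may be post-drug. The laboratory exposure is mainly in hematology.

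The size of any bias cannot be estimated from the documents. The 60 of 72 permitted hours assumes that ICU return coincides with the transplant reference time; the share falls to 67% if return is 12 hours later. Actual draw times could all precede the infusion. The primary endpoint and its analysis are not affected. The correction is worth making because it is cheap and uses measurements the protocol already requires. It also supports the two summaries that carry information adverse event collection leaves out.

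**What to change.** 1. **SAP 8.4:** define baseline as the last value before the start of the first infusion, using the section 6.2 CBC and metabolic panel. Where an analyte is not in that panel, the same rule falls back to the latest earlier value, such as visit 00.
2. **Data capture:** enter the section 6.2 results with draw and infusion start times. Flag visit 01 samples drawn after infusion start and do not use them as baseline.
3. **SAP 8.5.1:** replace the sentence saying that pre-infusion vitals are not collected. Enter the pre-infusion and in-infusion vitals on the infusion CRF and summarise change from pre-infusion by arm. Changing the SAP sentence alone would not create the data.
4. **Visit 02 sampling:** reconcile Appendix 1 footnote 3 with Table 11.
5. **First-dose wording:** section 6.1.1.3 (from the ICU) and sections 6.1.1.2 and 8.6 and SAP 6.2 (to the ICU) must be reconciled by the sponsor. No view is taken here on which is right.

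The cost is SAP and schedule wording, a few CRF fields for measurements already required, and some visit 01 samples that no longer count as baseline.
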